## PRÉCIS

Prevention of oral chronic graft versus host disease (GVHD) by topical agents is an attractive strategy because it would potentially avoid the adverse effects associated with systemic immunosuppression. Topically administered dexamethasone solution is a commonly used agent for the prophylaxis of oral inflammatory conditions including GVHD. However, the efficacy and systemic effects of topically administered dexamethasone solution are unknown. We therefore propose this trial designed to evaluate the efficacy and safety of topical dexamethasone solution for prevention of oral chronic GVHD in stem cell transplant recipients.

This pilot phase II study will follow a randomized, double-blind, placebo controlled, parallel group design. Consenting subjects who have undergone hematopoietic stem cell transplantation at the NIH Clinical Center and the surrounding transplant clinics will be randomized 50/50 to receive dexamethasone 0.01% solution or placebo as an oral rinse for 3 months starting 90-100 days post-transplant. Subjects will be evaluated monthly after the start of intervention. Diagnostic and research evaluations will include a complete oral examination, oral mucosal biopsy prior to the beginning of the intervention (day -7) and at the time of development of oral chronic GVHD or at the completion of intervention in the absence of clinical GVHD. We will measure serum dexamethasone levels and perform short cosyntropin (ACTH stimulation) test at the end of the 3 months of intervention or onset of clinically significant GVHD.

The primary objective of the study is to evaluate the safety and efficacy of topical dexamethasone 0.01% solution used as an oral rinse for prevention of oral chronic GVHD. Our primary endpoint will be the proportion of subjects that develop clinically significant (severity score 3 or higher) oral chronic GVHD after three months.

Secondary objectives will include the impact of oral chronic GVHD on the quality of life, characterization of the changes in tissue and salivary biomarkers associated with development of oral graft versus host disease, and measures of the effects of topical dexamethasone on hypothalamo-pituitary-adrenal axis. Secondary outcomes will include oral cavity specific quality of life as measured by OHIP-14 questionnaire, oral discomfort levels, improvement in general quality of life scores, and severity of oral chronic GVHD as measured by the site-specific GVHD scoring system.

---

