#### **6.1.2 Baseline assessments**

- Serum chemistry (Acute Care (Na, K, Cl, CO2, Creatinine, Glucose, and Urea Nitrogen), Mineral (Phosphorus, Magnesium, Albumin, and Calcium), Hepatic (Alk Phosphatase, ALT, AST, Total Bilirubin, and Direct Bilirubin), and Other (Total Protein, CK, Uric Acid, and LD) panel) done concurrently with post transplant monitoring
- Pregnancy test (females of child bearing potential)
- Serum cortisol level (results blinded to investigators)
- The 0-10 Scale for Oral Pain (see Appendix A)
- The 0-10 Scale for Oral Xerostomia (see Appendix A)
- GVHD Severity Scale (see Appendix B)
- Lichen Planus (Oral GVHD) Severity Scale (see Appendix C)
- Disease specific quality of life - OHIP-14 scale (ages 18 and older only-Appendix D)
- Oral photographs (Optional)
- Oral lesion documentation
- Buccal mucosal less than approximately 6mm punch biopsy (ages 18 and older only) (optional)
- Research blood sample collection
- Research saliva sample collection
- Growth chart (length for age, weight for age percentiles and body mass index for age percentiles, pre-pubertal children) (if a hand x-ray is available on parent transplant protocol, the results will be reviewed)

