## **8.7 Stopping Rule**

There will be no interim statistical analysis given the small preliminary nature of the study. We do not expect dramatic efficacy or significant difference in serious adverse effects that would require stopping the trial early. The study medication is a safe and non-toxic agent commonly used for the prophylaxis of oral chronic GVHD and other oral mucosal conditions. All the procedures specifically related to this protocol are standard diagnostic procedures and are associated with few complications. In the event of a serious adverse event related to the study medication or procedure the IRB will be notified immediately.

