### 9.2 Adverse Events

Because dexamethasone is an FDA approved drug with known toxicity profile, any observed or volunteered adverse events will not be captured in the database unless (1) the adverse event is previously unknown (not on the label) or more severe than on the label and deemed possibly, probably or definitely related to the study medication or (2) meets the criteria for a severe adverse event. Adverse events that are complications of the primary transplant protocol and deemed unlikely or unrelated to dexamethasone will not be captured in the database for this protocol, but will be collected and reported in the transplant protocol. The collection of AE information will begin on the first day of initiation of the study drug.

The NCI Common Terminology Criteria for Adverse Events Version 4 (CTCAE) will be used for toxicity and adverse event reporting. All appropriate treatment areas have access to a copy of the CTCAE version 4.0. A copy of the CTCAE version 4.0 can be downloaded from the CTEP web site (<http://ctep.cancer.gov>).

**Adverse event** is defined according to 21 (CFR 312.32(a)) as any untoward medical occurrence associated with the use of a drug in humans, whether or not considered drug related. An adverse event can also be any unfavorable and unintended diagnosis, symptom, sign (including an abnormal laboratory finding), syndrome, or disease temporally associated with the use of a drug, without any judgment about causality. Adverse event either occurs during the study participation, having been absent at baseline or if present at baseline, appears to worsen.

An abnormal laboratory value will be considered an AE if the laboratory abnormality is characterized by any of the following:

- Results in discontinuation from the study
- Is associated with clinical signs or symptoms
- Requires treatment or any other therapeutic intervention
- Is associated with death or another serious adverse event, including hospitalization
- Is judged by the Investigator to be of significant clinical impact
- If any abnormal laboratory result is considered clinically significant, the investigator will provide details about the action taken with respect to the test drug and about the patient's outcome.

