### **9.3 Serious Adverse Events**

A serious adverse event is any untoward medical occurrence that:

- results in death
- is life-threatening, requires or prolongs hospitalization
- causes persistent or significant disability/incapacity
- results in congenital anomalies/birth defects
- or in the opinion of the investigators represents other significant hazards or potentially serious harm to research subjects or others.

Only those SAEs that are determined possibly, probably or definitely related to this protocol will be reported on this ancillary study. Those determined possibly, probably or definitely to post transplant complications will be reported on the transplant protocol.

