#### 10.3.4 Related to tissue biopsy

Oral mucosal punch biopsy is a minor surgical procedure that may be associated with temporary bleeding, hematoma at the site, local infection and postoperative discomfort. These risks are small (generally <5%) and transient.

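### The adverse-event capture rule in Section 9.2 does not match the protocol's own serious-event reporting, and it leaves out non-serious complications of the research biopsies

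*Combined protocol and SAP*

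**What the plan says.** Section 9.2 restricts what enters the database, on the ground that dexamethasone is approved and its toxicity is known. There are two ways in. Criterion (1) takes events that are not on the label, or are worse than labelled, and are judged "possibly, probably or definitely related to the study medication". Criterion (2) takes an event that "meets the criteria for a severe adverse event". The same section fixes the start: "The collection of AE information will begin on the first day of initiation of the study drug". It adopts CTCAE version 4 for grading. It leaves complications of the transplant that are judged not related to dexamethasone to the transplant protocol.

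Section 9.3 then gives an outcome-based list under a different term: "A serious adverse event is any untoward medical occurrence that" results in death, hospitalisation and so on. Section 8.7 adds: "In the event of a serious adverse event related to the study medication or procedure the IRB will be notified immediately".

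The Précis describes "oral mucosal biopsy prior to the beginning of the intervention (day -7"), and Section 6.1.2 lists it as "Buccal mucosal less than approximately 6mm punch biopsy (ages 18 and older only) (optional"). Section 10.3.4 names bleeding, haematoma, infection and discomfort as the biopsy's risks and says: "These risks are small (generally <5%) and transient".

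Section 8.2 counts subjects who develop oral GVHD between baseline and first dose among the drop-outs, and says that drop-outs' safety data enter the safety analysis. Section 8.5 tabulates adverse events by severity and arm.

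**The concern.** Safety is half of the primary objective (Section 1.1), and the table in 8.5 can show only what 9.2 lets in. Two features of 9.2 do not fit the rest of the protocol.

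First, *severe* describes intensity and *serious* describes outcome. Criterion (1) shuts out known steroid effects at their expected severity, so for those events criterion (2) is the only way in. If it is applied as an intensity threshold, the database and the serious-event reports will hold different sets of events, and the final table may omit events already reported during the trial.

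Second, the reason given for restricted capture, a well-known drug, does not extend to research biopsies. Their non-serious complications have no capture criterion at any visit and, before first dose, no collection period. The safety data that 8.2 promises for subjects lost before first dose would then largely not exist.

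**Working it through.** The point rests mainly on text. The plan states no figure for it that could be reproduced.

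**Step 1: which events get in.** I read the relatedness condition in criterion (1) as applying to both unlabelled and worse-than-labelled events, and I take the database to be the source of the table in 8.5, which names no source.

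| Event | Criterion (1) | Criterion (2), read literally | Reporting route elsewhere |
|---|---|---|---|
| Drug-related, labelled, serious but not severe in grade | No: labelled | No: not severe | Yes: 9.3, 9.4, 8.7 |
| Biopsy-related, serious, after first dose | No: not drug-related | Only if also severe | Yes: 9.3, 9.4, 8.7 |
| Biopsy-related, serious, before first dose | Collection not open | Collection not open | Yes: none of these sections sets a start at first dose |
| Biopsy-related, not serious or severe, after first dose | No: not drug-related | No | None as an adverse event |
| Biopsy-related, not serious or severe, before first dose | Collection not open | Collection not open | None as an adverse event |

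If *severe* is read as *serious*, the first two rows enter the database. The last two stay out on either reading. Moving the start date alone would not bring in the last row, because it would still fail criterion (1).

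**Step 2: size of the pre-dose gap.** Inputs:

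- maximum accrual of 82 (Section 8.2);
- complication risk *p* with a stated ceiling of 5% (Section 10.3.4), where values down to 1% are my assumption;
- number of baseline biopsies *n*, with uptake of 25% to 100% of 82 assumed, because the biopsy is optional and no uptake is given.

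Expected events = *n* × *p*. Probability of at least one = 1 − (1 − *p*)^*n*.

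| Uptake | *n* | Expected at 5% | P(≥1) at 5% | Expected at 1% | P(≥1) at 1% |
|---|---|---|---|---|---|
| 100% | 82 | 82 × 0.05 = 4.1 | 0.985 | 0.82 | 0.561 |
| 93% | 76 | 3.8 | 0.980 | 0.76 | 0.534 |
| 50% | 41 | 2.05 | 0.878 | 0.41 | 0.338 |
| 25% | 20 | 1.0 | 0.642 | 0.2 | 0.182 |

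The 93% row is the most that adults-only biopsy allows if 7% of subjects are minors, as Section 10.1 expects. The range is about 0.2 to 4 events.

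**Step 3: length of the uncovered period.** From the biopsy at day −7 it is about a week. Section 7.1 also lists research blood and saliva at the screening appointment. Screening can be as early as day 60 after transplant (Section 6.1.1), and drug starts at day 90–100 (Précis). Counted from a screening sample, the period could reach 100 − 60 = 40 days.

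**The case against.** A reader might infer from 9.2 that serious events go unrecorded, including serious biopsy complications. The documents do not support that. Section 9.4 sends every serious event to the principal investigator, 9.3 reports those related to this protocol, and 8.7 sends those related to a study procedure to the IRB. None of these is limited to the period after first dose. Section 8.7 therefore helps to fill the gap. What can be lost is entry in the analysed data, not the report.

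It can also be said that *severe* is simply a slip. Criterion (2) refers to criteria, and the only list of such criteria is the one for *serious* in the next section. That is plausible, but 9.2 also names a grading scale, so a data manager could reasonably apply an intensity threshold. A slip in an operative rule still needs correcting.

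Three further points stand. The figure of about 4 events is a ceiling: it needs every subject to accept an optional, adults-only biopsy and the risk to equal the stated maximum. Events before first dose cannot be caused by the rinse, so their absence does not bias the comparison between arms. And restricted capture for a known drug is a legitimate choice, with transplant complications collected elsewhere. That rationale does not cover the protocol's own research procedures.

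**Conclusion.** The concern holds as a mismatch between database capture and safety reporting. It is not a failure to report serious events. On a literal reading of 9.2, a labelled event that is serious but not severe is reported and yet can be absent from the table in 8.5. How many such events there would be cannot be estimated from the documents.

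On either reading, non-serious complications of the research biopsies stay out of the database, before and after first dose. The pre-dose part comes to about 0.2 to 4 events, resting on assumed uptake of 25–100% and risk of 1–5%; by the protocol's own description they are mostly minor and transient. The conflict with 8.2 over subjects lost before first dose stands.

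The efficacy analysis is untouched. The mismatch of terms and the missing procedure criterion are worth correcting; the pre-dose window alone would be a minor point.

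**What to change.** Make three changes to Section 9.2:

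1. In criterion (2), replace *severe adverse event* by *serious adverse event (Section 9.3)*, so that every serious event reported on this study is also in the analysed data. The exclusion for unrelated transplant complications can stay.
2. Add a criterion (3) for events possibly, probably or definitely related to a study procedure.
3. Start collection of procedure-related events at the first protocol-specific research procedure. In 8.5, tabulate pre-dose events separately, so that the table from first dose onward still serves the comparison between arms.

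Changes 2 and 3 are needed together: an earlier start without a procedure criterion captures no non-serious biopsy events. The cost is a short amendment and a modest amount of extra recording before first dose. That is about a week per subject if counted from the day −7 biopsy, and possibly up to about 40 days if a research sample taken at screening counts as the first procedure. The amendment should say which of the two applies.

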### **9.3 Serious Adverse Events**

A serious adverse event is any untoward medical occurrence that:

- results in death
- is life-threatening, requires or prolongs hospitalization
- causes persistent or significant disability/incapacity
- results in congenital anomalies/birth defects
- or in the opinion of the investigators represents other significant hazards or potentially serious harm to research subjects or others.

Only those SAEs that are determined possibly, probably or definitely related to this protocol will be reported on this ancillary study. Those determined possibly, probably or definitely to post transplant complications will be reported on the transplant protocol.

### **9.4 Serious Adverse Events Reporting**

**PI:** All serious adverse events will be reported to [name]., Principal Investigator and Medically Responsible Investigator

[name].  
[name]  
[contact]

**NHLBI DSMB:** Reports of serious adverse events that are unexpected and thought to be possibly, probably or definitely related to this protocol to be reported on this ancillary study will also be forwarded no later than seven (7) days in the case of death or life-threatening serious adverse events or within fifteen (15) days after the occurrence of all other forms of serious adverse events to the Data and Safety Monitoring Board (DSMB). All SAEs that are considered at least possibly related to the study agent will be included for reviewed by the DSMB.

SAEs determined to be related to post transplant complications will be reported on the transplant protocol.

### **9.5 Unanticipated Problems and Protocol Deviations**

An unanticipated problem is any incident, experience, or outcome that is:

1. unexpected in terms of nature, severity, or frequency in relation to:

- a) the research risks that are described in the IRB-approved research protocol and informed consent document, Investigator's Brochure or other study documents, and
- b) the characteristics of the subject population being studied, and

- 2.related or possibly related to participation in the research, and
- 3.places subjects or others at a greater risk of harm (including physical, psychological, economic, or social harm) than was previously known or recognized. (An AE with a serious outcome will be considered increased risk.)

A protocol deviation is any change, divergence, or departure from the study design or procedures of an IRB-approved research protocol.

## **Reports to the IRB and CD**

### **Expedited Reporting**

Events requiring expedited reporting (serious protocol deviations, unanticipated problems, instances of non-compliance) will be submitted to the IRB per Policy 801 “Reporting Research Events”.

### **Reports to the IRB at the time of Continuing Review:**

The PI or designee will refer to HRPP Policy 801 “Reporting Research Events” to determine IRB reporting requirements.

### **Reports to the CD:**

The PI or designee will refer to NHLBI DIR Policy to determine CD reporting requirements and timelines.

# **10. HUMAN SUBJECT PROTECTIONS**

## **10.1 Rationale for Subject Selection**

No subjects will be excluded from participation based on gender, race or ethnicity. The study will be open to all subjects who satisfy the inclusion criteria and provide an informed consent to the protocol. From previous transplant protocol recruitment patterns at NIH we expect the population may be distributed as follows:

- by gender: 40% females; 60% males
- by age: ages 11-73, median 38; 7% ages 10-17; 20% ages 18-30; 28% ages 31-40; 22% ages 41-50 and 23% ages 51-73
- by race/ethnicity: 11% Asian, 8% Black, 44% Hispanic, 37% White

Recruitment: Subjects will be recruited from NIH Clinical Center and the surrounding hematopoietic stem cell transplant clinics.

**Reimbursement for protocol participation, travel, food, and lodging:** Reimbursement will occur on this protocol; subject reimbursement will be according to the NHLBI travel policy reimbursement and will be consistent with NIH and NHLBI guidelines.

## **10.2 Participation of Children**

When a pediatric subject reaches age 18, continued participation will require consenting of the now adult with the standard protocol consent document to ensure legally effective informed consent has been obtained. Should sample or data analysis continue following completion of active participation and the subject has reached 18 years of age, we will attempt to contact the subject using the last known contact information to obtain consent for continued use of data or samples collected during their prior visit. Given the length of

time that may have transpired for some of the subjects since their last visit for this study, we request waiver of informed consent for those individuals who after good faith efforts to contact them, we are unable to contact.

Requirements for Waiver of Consent consistent with 45 CFR 46.116 (d), each of which must be addressed in relation to the protocol:

- (1) The research involves no more than minimal risk to the subjects;
  - a) Analysis of samples and data from this study involves no additional risks to subjects.
- (2) The waiver or alteration will not adversely affect the rights and welfare of the subjects;
  - a) Samples and data will be kept in secure locations in the laboratory of [name]. Retention of samples or data does not affect the welfare of subjects.
- (3) The research could not practicably be carried out without the waiver or alteration; and
  - a) Considering the length of time between a minor's enrollment and their age of majority, it is possible that more than a few subjects may be lost to follow up. A significant reduction in the number of samples analyzed could impact the quality of the research.
- (4) Whenever appropriate, the subjects will be provided with additional pertinent information after participation.
  - a) We only plan to request a waiver of re-consent for those subjects who have been lost to follow-up.

If the subject is an affected minor (level of risk is Category 3), both parents must provide parental permission unless one parent is deceased, unknown, incompetent, or not reasonably available (i.e., incarcerated), or when only one parent or guardian has legal responsibility for the care and custody of the child. In the event that one parent is not present to provide consent, telephone consent from one parent may be obtained.

If the subject is an unaffected minor (level of risk is Category 1) we request that only one parent be required to provide parental permission. However, in cases where parents share joint legal custody for medical decisions for a child (e.g., by custody agreement or court order), both parents must give their permission regardless of the level of risk of the research. Exceptions may be made if one parent has since died, become incompetent, or is not reasonably available (e.g., incarcerated).

This study will be limited to subjects aged 12 or older. Given the preliminary nature of the study and requirement for precise compliance with the instructions to minimize swallowing and systemic absorption of dexamethasone, children < 12 who are less likely to comply will be excluded. In addition, oral rinses such as topical fluorides are not recommended for young children; and children < 12 are less likely to develop GVHD. Oral biopsy for research purposes will be limited to subjects 18 years old and older.

Pregnancy testing will be done in all females of childbearing potential. We will inform any applicable minors during the assent process that for safety, we need to do a pregnancy test. She will be told that if the pregnancy test is positive, we will counsel her and help her tell her parents if she wishes. If the minor does not want to proceed, she will be advised not to sign the assent and her study participation will end.

